13.2.3 Investigator Compliance

No modifications to the protocol will be made without the approval of both the investigator and Vertex. Changes that significantly affect the safety of the subjects, the scope of the investigation, or the scientific quality of the study (i.e., efficacy assessments) will require IRB/IEC notification before implementation, except where the modification is necessary to eliminate an apparent immediate hazard to subjects. Vertex will submit all protocol modifications to the required regulatory authorities.

When circumstances require an immediate departure from procedures set forth in the protocol, the investigator will contact Vertex to discuss the planned course of action. If possible, contact will be made before the implementation of any changes. Any departures from the protocol will be fully documented in the source documentation and in a protocol deviation log.

13.2.4 Access to Records

The investigator will make the office and/or hospital records of subjects enrolled in this study available for inspection by Vertex or its representative at the time of each monitoring visit and for audits. The records will also be available for direct inspection, verification, and copying, as required by applicable laws and regulations, by officials of the regulatory health authorities (FDA and others). The investigator will comply with applicable privacy and security laws for use and disclosure of information related to the research set forth in this protocol.

13.2.5 Subject Privacy

To maintain subject confidentiality and to comply with applicable data protection and privacy laws and regulations, all CRFs, study reports, and communications relating to the study will identify subjects by assigned subject numbers and access to subject names linked to such numbers shall be limited to the site and the study physician and shall not be disclosed to Vertex. As required by applicable laws and regulations in the countries in which the study is being conducted, the investigator will allow Vertex and/or its representatives access to all pertinent medical records to allow for the verification of data gathered in the CRFs/SAE forms and the review of the data collection process. The FDA and regulatory authorities in other jurisdictions, including the IRB/EC, may also request access to all study records, including source documentation, for inspection.

For sites participating in the study in the US, and in accordance with the Health Insurance Portability and Accountability Act (HIPAA) and associated regulations, an executed HIPAA authorization shall be obtained by the site from each subject (or the legal representative of the subject) before research activities may begin. Each HIPAA authorization shall comply with all HIPAA requirements including authorization allowing the site access to and use of the subject's personally identifiable health information, authorization for the site to disclose such information to Vertex, the FDA, and other parties requiring access under the protocol, and statements as to the purpose for which such information may be used and for how long.

13.2.6 Record Retention

The investigator will maintain all study records according to ICH GCP guidelines and/or applicable local regulatory requirement(s), whichever is longest, as described in the Clinical Trial Agreement. If the investigator withdraws from the responsibility of keeping the study records, custody will be transferred to a person willing to accept the responsibility and Vertex will be notified.

13.2.7 Study Termination

At any time, Vertex may terminate this study in its entirety or may terminate this study at any particular site. In addition, for reasonable cause, either the investigators or their IRBs/IECs may terminate the study at their center.

Conditions that may lead to reasonable cause and warrant termination include, but are not limited to:

- Subject or investigator noncompliance

- Unsatisfactory subject enrollment
- Lack of adherence to protocol procedures
- Lack of evaluable and/or complete data
- Potentially unacceptable risk to study subjects
- Decision to modify drug development plan
- Decision by the FDA or other regulatory authority

Written notification that includes the reason for the clinical study termination is required.

13.3 Data Quality Assurance

Vertex or its designated representative will conduct a study site visit to verify the qualifications of each investigator, inspect clinical study site facilities, and inform the investigator of responsibilities and procedures for ensuring adequate and correct study documentation.

The investigator is required to prepare and maintain adequate and accurate case histories designed to record all observations and other data pertinent to the study for each study participant. Study data for each enrolled subject will be entered into a CRF by study site personnel using a secure, validated, web-based electronic data capture (EDC) application. Vertex will have read-only access to site-entered clinical data in the EDC application.

Instances of missing, discrepant, or uninterpretable data will be queried with the investigator for resolution. Any changes to study data will be made to the CRF and documented in an audit trail, which will be maintained within the clinical database.

13.4 Monitoring

Monitoring and auditing procedures developed or approved by Vertex will be followed to comply with GCP guidelines. On-site checking of the CRFs/SAE Forms for completeness and clarity, cross-checking with source documents, and clarification of administrative matters will be performed.

The study will be monitored by Vertex or its designee. Monitoring will be done by personal visits from a representative of Vertex, or designee (study site monitor), who will review the CRFs/SAE Forms and source documents. The study site monitor will ensure that the investigation is conducted according to the protocol design and regulatory requirements.

13.5 Electronic Data Capture

Vertex will provide the study sites with secure access to and training on the EDC application sufficient to permit study site personnel to enter or correct information in the CRFs on the subjects for which they are responsible.

[figure not shown]
A CRF will be completed for each enrolled study subject. It is the investigator's responsibility to ensure the accuracy, completeness, clarity, and timeliness of the data reported in the subject's CRF. Source documentation supporting the CRF data will indicate the subject's participation in the study and will document the dates and details of study procedures, AEs, other observations, and subject status.

The investigator, or designated representative, will complete the CRF as soon as possible after information is collected.

The audit trail entry will show the user's identification information and the date and time of any correction. The investigator will provide formal approval of all the information in the CRFs, including any changes made to the CRFs, to endorse the final submitted data for the subjects for whom the investigator is responsible.

Vertex will retain the CRF data and corresponding audit trails. A copy of the final archival CRF in the form of a CD or other electronic media will be placed in the investigators study file.

13.6 Publications and Clinical Study Report

13.6.2 Clinical Study Report

A clinical study report, written in accordance with the ICH E3 Guideline, will be submitted in accordance with local regulations.

3 INTRODUCTION

Study VX15-661-112 is a phase 2, randomized, placebo-controlled, double-blind study to evaluate the effect of vx-661 in combination with ivacaftor on chest imaging endpoints in subjects aged 12 years and older with cystic fibrosis, homozygous for the *F508del CFTR* mutation.

This statistical analysis plan (SAP) Methods is based on the approved clinical study protocol (CSP), dated 26 February 2018, version 5.0. This SAP addresses the efficacy and safety objective of the study and describes the planned statistical analyses and data presentations for the CSR.

[figure not shown]
Vertex Biometrics department or a designated Contract Research Organization (CRO) will perform the statistical analysis of the safety and efficacy data. SAS[®] Version 9.4 Software (SAS Institute, Cary, North Carolina, USA) or higher will be used to generate all statistical outputs (tables, figures, listings, and datasets). The SAP will be finalized and approved prior to final database lock.

[figure not shown]
4 STUDY OBJECTIVES

4.1 Primary Objective(s)

- To evaluate the treatment effect of VX-661 in combination with ivacaftor (VX-661/ivacaftor) on chest imaging endpoints as evaluated using low-dose computed tomography (LDCT) at Week 72 in subjects with CF who are homozygous for the *F508del* mutation on the CF transmembrane conductance regulator (*CFTR*) gene

4.2 Secondary Objectives

- To evaluate the safety of VX-661/ivacaftor through Week 72
- 

5 STUDY ENDPOINTS

[figure not shown]
5.1 Efficacy Endpoints

- Absolute change in Total Brody/CF-CT score from baseline at Week 72 using LDCT.

5.2 Safety Endpoints

The safety and tolerability is evaluated via the following endpoints:

- Adverse events (AEs)
- Clinical laboratory values (hematology, serum chemistry, coagulation studies, vitamin levels, lipid panel, and urinalysis)
- Standard digital electrocardiograms (ECGs)
- Vital signs
- Pulse Oximetry

6 STUDY DESIGN

6.1 Overall Design

This is a Phase 2, randomized, placebo-controlled, double-blind parallel-group, multicenter study in subjects with CF who are homozygous for the *F508del-CFTR* mutation. This study is designed to evaluate the treatment effect of VX-661/ivacaftor on chest imaging endpoints during 72 weeks of treatment. LDCT [REDACTED] will be used for chest imaging. The images will be evaluated using the Brody/CF-CT scoring system. Safety over 72 weeks of treatment will also be evaluated.

Figure 6-1 shows a schematic of the study design. This study includes a Screening Period, a 72-week Treatment Period, and a Safety Follow-up Visit. Following a 28-day screening period, approximately 40 subjects will be randomized (1:1) to 1 of the 2 treatment arms, active or placebo, on Day 1.

[figure not shown]
The active treatment regimen will be comprised of a morning dose of a fixed-dose combination (FDC) tablet of VX-661 100-mg/ivacaftor 150-mg and an evening dose of

ivacaftor 150-mg to be taken approximately 12 hours after the morning dose. The placebo regimen will be visually-matched tablets to be taken on the same schedule as the active treatment.

The study will be double-blind. Subjects who complete the study may have the opportunity to receive VX-661/ivacaftor, provided they meet criteria, until VX-661/ivacaftor is commercially available to them or development is terminated. After completing Study VX15-661-112 (Study 112), subjects who meet the criteria may have the opportunity to participate in future Vertex programs with VX-661/ivacaftor, which may include additional scans.

Figure 6-1 VX15-661-112: Study Design

CT: computed tomography; [REDACTED]

6.2 Sample Size and Power

The primary endpoint is the absolute change from baseline of Total Brody/CF-CT score measured by the Brody/CF-CT score system at Week 72 using LDCT. The difference between the VX-661/ivacaftor group and the placebo group in the mean change from baseline in Total Brody/CF-CT score at Week 72 will be estimated.

This is an exploratory, Phase 2 study; the sample size is not based on statistical power. With 40 subjects (20 per arm), the study is aimed to explore changes in the Total Brody score over a 72 week period and for VX-661/ivacaftor versus placebo, based on the published literature^{1,2}.

6.3 Randomization

Approximately 40 subjects who meet the eligibility criteria will be randomized (1:1) to 1 of 2 treatment arms.

An interactive web response system (IWRS) will be used to assign subjects to treatment. The IWRS will use a list of randomization codes generated by a designated vendor [REDACTED].

6.4 Blinding

This is a double-blind study.

Imaging Data Blinding

Despite treatment blinding, knowledge of the LDCT [REDACTED] results has the potential to suggest whether a subject has been administered active study drug or placebo. Therefore, during the conduct of the study, the Vertex study team will have no access to the postdose imaging data. The vendor for central reading of the imaging data will send only the blinded files (blinded treatment group, with real scores for baseline, but with dummy scores for all the imaging assessments after baseline) to Vertex to be used for developing the statistical programs. Furthermore, subjects and their caregiver should not be informed of their study-related imaging results during the Treatment Period regardless of whether the subject has prematurely discontinued treatment.

CT scans [REDACTED] will have a clinical over-read by a site radiologist blinded to study drug assignment. Any urgent safety-related findings should be communicated to the Vertex medical monitor, who may recommend follow-up by the site principal investigator. The Vertex medical monitor will facilitate any discussion with the central readers as needed.

7 ANALYSIS SETS

The **All Subjects Set** is defined as all subjects who have been randomized or have received at least 1 dose of study medication. This analysis set will be used in subject listings and disposition summary table, unless otherwise specified.

The **Full Analysis Set (FAS)** is defined as all randomized subjects who have received at least 1 dose of study drug. The FAS is to be used in efficacy analyses in which subjects will be analyzed according to their randomized treatment group.

The **Safety Set** is defined as all subjects who received at least 1 dose of study drug. The Safety Set is to be used for all safety analyses in which subjects will be analyzed according to the treatment they received.

8 STATISTICAL ANALYSIS

8.1 General Considerations

The Schedule of Assessments is provided in [Appendix A \(Section 10.1\)](#).

All individual subject data for those randomized or exposed to study drug will be presented in data listings.

Continuous variables will be summarized using the following descriptive summary statistics: the number of subjects (n), mean, standard deviation (SD), standard error (SE), median, minimum value (min), and maximum value (max).

Categorical variables will be summarized using counts and percentages.

Baseline Value, unless otherwise specified, is defined as the most recent non-missing measurement (scheduled or unscheduled) collected prior to the first dose of study drug. For ECGs, the baseline will be defined as the average of the 3 pretreatment measurements (triplicate) on Day 1.

Absolute Change from baseline will be calculated as Postbaseline value - Baseline value.

Relative change from baseline will be calculated and expressed in percentage as $100\% \times (\text{Postbaseline value} - \text{Baseline value}) / \text{Baseline value}$.

Treatment Emergent (TE) Period will include the time from the first dose to Safety Follow-up Visit. For subjects who do not have a Safety Follow-up Visit because they rolled over into the open-label extension study within 28 days after the last dose of study drug, the end of the TE period will be the date of rollover into the extension study. For subjects who do not have a Safety Follow-up Visit and did not roll over into the extension study, the end of the TE period will be 28 days after the date of last dose. The TE period will be used for safety analyses unless otherwise specified.

Unscheduled Visits: Unscheduled visit measurements will be included in the analysis as follows:

- In scheduled visit windows per specified visit windowing rules;
- In the derivation of baseline and last on-treatment measurements;
- In the derivation of maximum/minimum on-treatment values and maximum/minimum changes from baseline values for safety analyses;
- In individual subject data listings where appropriate.

Visit Windowing Rules: The analysis visit windows for protocol-defined visits are provided in [Appendix B \(Section 10.2\)](#). The windows will be applied using the following rules for both scheduled and unscheduled visits:

1. If no measurement is available within a visit window, the assessment will be considered missing for the visit;
2. If there is more than one measurement available within the same visit window, use the following rules:

For all efficacy parameters, if there are multiple measurements within a visit window, the record at the scheduled visit will be used. Otherwise,

- If there are no measurements at the scheduled visit, then the record closest to the target day will be used;

- If there are multiple records with the same distance to the target day, the latest record will be used.
- Assessments at early treatment termination (ETT) visit will follow the windowing rules for regular visits up to Week 72.
- Assessments at safety follow-up (SFU) visit will follow the windowing rules for regular visits if it falls within the upper boundary of the window for Week 72, or remain as SFU if it goes beyond the upper boundary of the window for Week 72.

For all safety parameters, if there are multiple measurements within a visit window, then 1) the record closest to the target day will be used; 2) if there are multiple records within the same distance from the target day, the latest record will be used; or 3) SFU visit will not be windowed, instead, used per nominal visit in relevant analyses.

Incomplete/Missing data will not be imputed, unless otherwise specified.

Outliers: No formal statistical analyses will be performed to detect or remedy the presence of statistical outliers, unless otherwise specified.

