8.1.4 Early Termination of Treatment

If the subject prematurely discontinues study drug treatment, an Early Termination of Treatment (ETT) Visit should be scheduled as soon as possible after termination of study drug treatment. Subjects who prematurely discontinue treatment will also be required to complete the Safety Follow-up Visit, approximately 28 (\pm 7) days after their last dose of study drug. The assessments performed at the ETT Visit and Safety Follow-up Visit are listed in [Table 3-2](#).

The ETT Visit should occur within 7 days after the last dose of study drug. If the ETT Visit occurs 3 weeks or later following the last dose of study drug, then the ETT Visit will replace the Safety Follow-up Visit, and a separate Safety Follow-up Visit will not be required.

During the course of study conduct, if VX-661 in combination with ivacaftor is approved by local health authorities and is available for the treatment of the population enrolled in this study, subjects may be discontinued from this study at the discretion of the sponsor ([Section 10.6](#)). If a subject is continuing onto commercially available VX-661/ivacaftor, the ETT Visit will be completed before dosing with commercially available drug begins, and the Safety Follow-up Visit will not be required.

Alternatively, if after review of a marketing application, local health authorities decline to approve, or if clinically meaningful benefit is not demonstrated for the use of VX-661/ivacaftor for the treatment of CF in populations enrolled in this study, subjects within those populations may be discontinued after communication to investigators and institutional review boards (IRBs)/independent ethics committees (IECs) of the risks/benefits related to the safety and efficacy. If subjects are discontinued from the study, an ETT Visit should occur within 7 days after the last dose of study drug and a Safety Follow-up Visit should occur within 28 (\pm 7) days after the last dose of study drug.

If the subject withdraws from the study and also withdraws consent for disclosure of future information, no further evaluations should be performed and no additional data should be collected. Vertex may retain and continue to use any data collected before such withdrawal of consent.

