10.6 Discontinuation of Study Participation

If after review of a marketing application, local health authorities decline to approve, or if clinically meaningful benefit is not demonstrated for the use of VX-661/ivacaftor for the treatment of CF in populations enrolled in this study, subjects within those populations may be discontinued after communication to investigators and IRBs/IECs of the risks/benefits related to the safety and efficacy. In addition, if evaluation of efficacy data from the Phase 3 studies (Studies VX14-661-106, VX14-661-107, VX14-661-108, and VX14-661-109) suggest that the VX-661/ivacaftor treatment does not provide clinically meaningful benefit, Vertex may recommend that subjects are discontinued or the study is terminated (see [Section 13.2.7](#)).

Subjects who are able to receive commercially-available VX-661/ivacaftor by prescription of a physician may be discontinued from the study at the discretion of the sponsor. If a subject is continuing onto commercially available VX-661/ivacaftor, the ETT Visit ([Section 8.1.4](#)) will be completed before dosing with commercial drug begins, and the Safety Follow-up Visit ([Section 8.1.3](#)) will not be required.

A subject may be discontinued at any time due to safety reasons. If a subject discontinues study drug, he/she should complete the ETT Visit ([Section 8.1.4](#)) and Safety Follow-up Visit ([Section 8.1.3](#)).

If during the time when a subject is participating in the study a cataract or lens opacity is identified and determined to be clinically significant by the ophthalmologist after dosing, discussion as to that subject's continuance in the study is provided in [Section 11.6.8](#).

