12.3.1 General Considerations

Continuous variables will be summarized using the following descriptive summary statistics: the number of subjects (n), mean, standard deviation (SD), standard error (SE), median, minimum value (min), and maximum value (max).

Categorical variables will be summarized using counts and percentages.

Baseline value, unless otherwise specified, is defined as the most recent nonmissing measurement (scheduled or unscheduled) collected before the first dose of study drug. For ECGs, the baseline will be defined as the average of the 3 pretreatment measurements (triplicate) on Day 1.

Change (Absolute Change) from baseline will be calculated as Postbaseline value - Baseline value.

Relative change from baseline will be calculated and expressed in percentage as $100\% \times \frac{\text{Postbaseline value} - \text{Baseline value}}{\text{Baseline value}}$

Treatment-emergent (TE) Period will include the time from the first dose to the Safety Follow-up Visit or 28 days after the last dose of the study drug for subjects who do not have a Safety Follow-up Visit. The TE period will be used for safety analyses unless otherwise specified.

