13.1.1.3 Documentation of Adverse Events

All AEs will be collected from the time ICF is signed until the following time points:

- For subjects who do not enroll: until time of screen failure (e.g., screen failure, withdrawal of consent)
- For enrolled subjects who have a Safety Follow-up Visit: through the Safety Follow-up Visit
- For enrolled subjects who do not have a Safety Follow-up Visit, the **earliest** of
 - 28 days after the last dose of study drug,
 - the ETT Visit, if that visit is 3 weeks or later following the last dose of study drug (see [Section 8.1.4](#)), or
 - before the first dose of study drug in another study (if applicable).

All subjects will be queried, using nonleading questions, about the occurrence of AEs at each study visit. When possible, a constellation of signs and/or symptoms will be identified as 1 overall event or diagnosis. All AEs for enrolled subjects will be recorded in the CRF and source document. AEs for subjects who are screened but not subsequently enrolled in the study will be recorded only in the subject's source documents. The following data will be documented for each AE:

- Description of the event
- Classification of “serious” or “nonserious”
- Date of first occurrence and date of resolution (if applicable)
- Severity
- Causal relationship to study drug(s)
- Action taken
- Outcome
- Concomitant medication or other treatment given

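### The treatment-emergent period stops at rollover into the extension but not at a switch to commercial VX-661/ivacaftor, so events on commercial active drug can be counted under placebo

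*SAP*

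**What the plan says.** SAP 8.1 gives the TE period three possible ends. The usual one is the Safety Follow-up Visit. For subjects who miss that visit because they entered the open-label extension (Study 110) within 28 days of last dose, "the end of the TE period will be the date of rollover into the extension study". For subjects with neither event, "the end of the TE period will be 28 days after the date of last dose". Protocol 12.3.1 has only the first and last of these; its fallback is "28 days after the last dose of the study drug for subjects who do not have a Safety Follow-up Visit", with no exception for the extension or for commercial drug.

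The commercial path is foreseen. Under Protocol 10.6, subjects who can obtain the marketed product on prescription "may be discontinued from the study at the discretion of the sponsor". Nothing limits this to one arm. Protocol 8.1.4 adds that for them "the ETT Visit will be completed before dosing with commercially available drug begins, and the Safety Follow-up Visit will not be required". On timing, the same section says: "The ETT Visit should occur within 7 days after the last dose of study drug".

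SAP 8.4.1 defines a treatment-emergent adverse event (TEAE) by time alone, from first dose to the end of the TE period. SAP 7 tabulates safety by treatment received, and Protocol 10 defines study drug as VX-661/ivacaftor and its matching placebo. For subjects without a Safety Follow-up Visit, Protocol 13.1.1.3 ends AE collection at the earliest of 28 days after last dose, an Early Termination of Treatment (ETT) Visit held 3 weeks or more after last dose, or the start of study drug in another study. Commercial drug is not among these stops.

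**The concern.** The extension and the commercial product pose the same attribution problem: a placebo subject may begin active drug while still inside the TE window. The SAP solves it for the extension by ending the window at rollover. It leaves the commercial path on the 28-day rule.

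An event arising on commercial active drug in a former placebo subject would then be a placebo TEAE. In a subject from the active arm, the days after last dose would be further time on active drug rather than time off it. Safety through Week 72 is a stated secondary objective, and the arms are small enough for a single misplaced subject to show in an incidence table.

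**Working it through.** The plan gives no figure to reproduce here, so the check traces the rules and then does the date arithmetic.

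**Tracing a placebo subject who switches**

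1. The ETT Visit is completed before commercial dosing, and no Safety Follow-up Visit is required (Protocol 8.1.4, 10.6). The first TE end does not apply.
2. The subject has not entered Study 110. The second TE end does not apply.
3. The TE period therefore ends 28 days after last study dose (SAP 8.1; the same under Protocol 12.3.1).
4. An on-time ETT Visit falls within 7 days of last dose, so commercial dosing can begin well inside the 28 days. The protocol sets no latest start.
5. A new event after that start but before day 28 meets the TEAE definition and is tabulated under placebo. By the timing rule in SAP 8.2.3 the commercial product would be a concomitant medication, which does not change the arm.

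**Days of overlap**

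Let g be the number of days from last study dose to first commercial dose. The documents do not give g; the values 1, 7 and 20 are assumptions.

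Overlap = 28 − g + 1 for g from 1 to 28, and 0 for g above 28.

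- g = 1: 28 − 1 + 1 = 28 days
- g = 7: 28 − 7 + 1 = 22 days
- g = 20: 28 − 20 + 1 = 9 days

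**Share of that subject's TE period**

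TE length = 7 × weeks on study drug + 28.

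| Last study dose | TE days | g = 1 | g = 7 | g = 20 |
|---|---|---|---|---|
| Week 12 | 84 + 28 = 112 | 25.0% | 19.6% | 8.0% |
| Week 24 | 168 + 28 = 196 | 14.3% | 11.2% | 4.6% |
| Week 48 | 336 + 28 = 364 | 7.7% | 6.0% | 2.5% |
| Just before Week 72 | 504 + 28 = 532 | 5.3% | 4.1% | 1.7% |

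The last row is for a subject who switches shortly before Week 72. Subjects who complete Week 72 are not on this path: their Safety Follow-up Visit is waived only for enrolment in Study 110 (Protocol 8.1.3).

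**Effect on an incidence table**

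With 20 subjects per arm (Protocol 12.1, SAP 6.2), one placebo subject whose only event arises on commercial drug adds 1/20 = 5 percentage points to placebo incidence.

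**The case against.** The best defence is that little would be captured. AEs are queried at study visits, and none is scheduled after an on-time ETT Visit. Table 3-2 likewise schedules no laboratory test or ECG after it for these subjects. What can enter the tables is a volunteered or serious event, an unscheduled measurement (which SAP 8.1 uses in visit windows and in maximum and minimum values), or data from a Safety Follow-up Visit held although not required. If the ETT Visit falls 3 weeks or later after last dose, it replaces the Safety Follow-up Visit and AE collection stops there, before commercial dosing. All of this stands, and it limits how often the gap matters. It does not close the gap.

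Table 9-1 prohibits commercial CFTR modulators through the Safety Follow-up Visit. That does not close it either, because Protocol 8.1.4 and 10.6 expressly provide for the switch and waive that visit.

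A reader might infer that the error always flatters the active arm. The documents do not show this. Starting active drug could add adverse effects but could also reduce disease-related events, and switching is open to both arms. A reader might also infer that scheduled laboratory and ECG data on active drug would be summarised under placebo; the visit schedule does not support that.

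Finally, the safety analysis is descriptive, the study is exploratory and the primary endpoint is untouched. That is true, and it keeps the point modest.

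**Conclusion.** The gap is real on the written rules. SAP 8.1 assigns time on commercial active drug to the arm of the study treatment whenever commercial dosing starts within 28 days of last study dose.

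It is conditional on approval, local availability, the sponsor's decision to discontinue the subject, and a prompt start of commercial drug. The overlap is anywhere from 0 to 28 days per switcher, and the number of placebo switchers may be anything from 0 to 20. A total of 20 × 28 = 560 patient-days would need the whole placebo arm to switch the day after last dose. It is a ceiling, not an expectation. The practical risk is a small number of misplaced events in a table where each affected subject can count for 5 percentage points. The sign of the net effect is unknown.

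**What to change.** In SAP 8.1, end the TE period at the earliest of: the Safety Follow-up Visit; the date of rollover into the extension; the day before the first dose of commercial VX-661/ivacaftor; or 28 days after last study dose. Align Protocol 12.3.1. With this rule the overlap falls to 0 for every value of g.

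Record the commercial start date explicitly. It cannot be assumed to be on file: Protocol 9.4 records medications through the Safety Follow-up Visit if applicable, and for switchers the last required visit comes before commercial dosing.

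Leave the AE collection window in Protocol 13.1.1.3 unchanged. Shortening it is not needed to correct attribution and would lose delayed events. List events that arise after the commercial start separately instead.

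The cost is one clause in each document, one extra date to collect, and up to 28 fewer post-dose days in the TEAE tables for each switcher.
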